
IMAGINE-POSITIVE (IMAGINE-P) is a novel and brief (4 sessions) school-based intervention for adolescent depression (Pile et al., 2018) that aims to increase access to early support and target the

underlying mechanisms of adolescent depression, using techniques of memory specificity and imagery re-scripting for negative events but also to bolster clear mental images of positive events. Initial findings from their case series (Pile et al., 2020) and feasibility RCT (Pile et al., 2021) suggest that imagery-based cognitive approaches are feasible for use with adolescents, improve mood and self-esteem, and are acceptable to young people. By adapting IMAGINE (Pile et al. (2018; 2020) and incorporating elements of other positive affect interventions, we have developed a novel and brief intervention for anhedonia in adolescent depression which aims to increase positive affect. Positive mental imagery is used to shift attention to positive affect (generating and savouring positive future goals and enhancing self-compassion) and manage the dampening appraisals which reduce positive affect (i.e. dampening appraisals).

Aims:

The primary aim of IMAGINE-P (Integrating Memories And Generating Images of New Experiences-Positive) is to develop a brief school-based intervention for young people that harnesses the ability to imagine positive future events in order to reduce anhedonia (improving positive affect) and to assess this for feasibility and acceptability. This structured intervention will be delivered face-to-face by a practitioner without extensive psychological training. A secondary aim will be to measure emotion regulation strategies deployed by young people to maintain positive affect during a universal stressor: the COVID19 pandemic. The project is a case series and feasibility randomised controlled trial (RCT) to refine the intervention manual and assess feasibility and acceptability. The RCT will also inform on whether a full-scale efficacy trial is warranted and will provide initial estimates of effect sizes.

Primary aims:

1. To develop a therapy manual that is brief, easy-to-access and appropriate to deliver online by a practitioner without extensive training. Development of the therapy manual includes a systematic review of the current treatments of anhedonia in depressed adult populations, as well as conducting a case series.

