2. To run a feasibility RCT to evaluate recruitment and retention rates for a future efficacy RCT, for example recruitment rates for schools and participants, attrition rates and outcome measure completion.
3. To assess the acceptability of the intervention to participants using post-therapy feedback questionnaires.

Secondary aims:

1. To gather descriptive data on symptom-change to inform sample size estimates for a future fully powered RCT of clinical and cost-effectiveness.
2. The secondary aim is to collect pilot data on clinical measures as well as on the underlying mechanisms proposed to be targeted in the intervention. This will include measures of imagery vividness, emotional response to positive future imagery and memory specificity.

Methods/ designs

Study design and timeline

In the case series all participants will receive the intervention. Participants will be recruited from multiple school/ college sites in the United Kingdom. Participants will be assessed at pre-intervention (prior to randomisation) and at follow-up, after the intervention, and at a 3-month follow-up after the intervention. For the feasibility randomised controlled trial, participants will be randomly allocated to either the intervention group or a control group (non-directive supportive therapy). Both of these are active interventions that aim to improve mood and self-esteem. Participants will also be recruited from multiple school/ college sites in the United Kingdom. Participants will be assessed at pre-intervention (prior to randomisation) and at follow-up, after the intervention, and at a 3-month follow-up after the intervention.

Study population

Inclusion criteria

1. Aged 14-19
2. Informed consent
3. Willing and able to engage in psychological therapy and complete assessments
4. Scoring above clinical cut-off on the MFQ (29 items; clinical cut-off ≥ 17), and showing high symptoms of anhedonia, as measured by the SHAPS (14 items; abnormal level of hedonic tone > 2)

Exclusion criteria

1. Diagnosis of learning disability (but not difficulty e.g. dyslexia), diagnosis of Autism Spectrum Disorder, or significant head injury, neurological disorder or epilepsy
2. Unable to fluently communicate in spoken English

3. Unable to give informed consent
4. High levels of current risk
5. Currently receiving therapy (including school counselling)

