6. Experiencing psychotic symptoms or depressed in the postnatal period (participants with co-morbid physical illness or non-psychotic disorders such as anxiety will not be excluded)

Setting

The intervention will be delivered face-to-face. The practitioner delivering the intervention will be working from a private workspace and participants will receive the intervention at school in a private designated space. Participants will complete their screen and assessment questionnaires online using Qualtrics.

Sample size

For the case series, 10 participants will be recruited. As the purpose of the trial is to assess feasibility and not efficacy, a power calculation to determine sample size is not appropriate. The data from this trial could however be used to inform a sample size calculation for a future efficacy trial. The target sample size (n=32; 16 in each arm) was determined with reference to good practice recommendations for feasibility/ pilot studies, which recommend sample sizes of between 24 and 50 (Julious, 2005; Lancaster, Dodd, & Williamson, 2004; Sim & Lewis, 2012). The sample size of 50 was inflated to allow for drop-out following randomisation, which was estimated to be 10% based on similar studies (Smith et al., 2015).

Recruitment (case series and trial), randomisation and blinding (trial only)

All participants will be recruited from a secondary school or sixth form college. The project researcher will liaise with the school gatekeeper and present the study to all students aged 16 to 18. All students will be provided with an information sheet at least 24 hours before the presentation to consider taking part. Following the presentation, all students will be invited to complete the screen questionnaire online if they wish to do so. At the screening stage we will ask the students' consent to inform the pastoral lead/ gatekeeper of their interest in the study, to ensure there is a private space at school for them to complete their sessions. Following the screen, eligible participants will be identified by scoring above clinical cut-off on the Mood and Feelings Questionnaire (MFQ) and showing high symptoms of anhedonia on the Snaith Hamilton Pleasure Scale (SHAPS). At the first assessment, the MFQ and SHAPS will be administered again, and participants will be assessed against the eligibility criteria. As participants will be over the age of 16, we will not seek parental

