The intervention will combine aspects of Memory Specificity Training (MeST), to educate on the links between memories and emotions, with Positive Prospective Mental Imagery (PPMI), to increase vividness and savouring of positive future images in order to harness positive affect. PPMI will first be introduced with a short-term goal that the participant wishes to complete in the next seven days. Participants will be guided to build up a detailed image of this goal, helping to increase imagery vividness, and are encouraged to engage in savouring techniques to bolster positive affect during the imagery generation. Dampening thoughts that may interfere with the image and reduce positive affect are identified. The role of self-critical thoughts are also explained and an imagery-based exercise for self-compassion is practiced. Participants then engage in PPMI for more long-term goals

to help identify practical steps towards their goals and anticipate any challenges or strengths along the way to achieving those goals. Lastly, participants link their specific memories and positive future images to their values.

Control intervention

Non-directive supportive therapy (NDST) will be delivered to participants in the control group, as it is a NICE recommended treatment for mild depression (NICE, 2019). NDST consists of individual sessions, whereby the practitioner is empathetic, emotionally supportive and provides non-directive problem solving and monitoring. Using NDST will control for factors that may contribute to change, which are not active components of IBCI-PA e.g. speaking to an empathetic therapist. Initial findings from a school-based feasibility RCT using NDST as the control intervention (Pile et al., 2020), found that NDST improved mood, suggesting it is more ethical for randomization than a waiting list control and reduced the potential for performance bias.

Treatment fidelity

Sessions will be audio recorded (if the young person provides consent). A sample of these sessions will then be assessed for adherence to the intervention manuals and competency by an independent rater. This will indicate whether there has been contamination between the two conditions due to the therapist being aware of both interventions.

Outcome measures

Primary

Feasibility data

- The number of eligible participants and willingness of schools and participants to take part
- Number of participants successfully completing intervention and reasons for drop-out

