- Time needed to collect (through online methods) and analyse data
- Data completeness and reasons for missing data
- Unexpected adverse effects
- Follow-up rates, adherence/ compliance rates and response rates to questionnaires at each time point (recruitment, intervention and follow-up).

Acceptability data

Participants will be asked to complete a feedback questionnaire about their experiences of the intervention itself and of it being delivered in school.

Secondary

Clinical outcome measures will be collected at baseline (pre), post and 3-month follow-up. These include measures of depression and anhedonia to measure the proposed mechanisms of therapeutic change.

- Mood and Feelings Questionnaire (MFQ) (Angold et al., 1995) is a 33-item measure of low mood in young people rated on a 3-point Likert scale. We have removed the risk items so will administer a 29-item version.
- Snaith-Hamilton Pleasure Scale (SHAPS) (Snaith et al., 1995) is a measure of anhedonia, consisting of 14 items rated on a 4-point Likert scale.
- Positive and Negative Affect Schedule (PANAS) (Watson, Clark & Tellegen, 1988) is a self-report measure of affect and consists of 20-items rated on a 5-point Likert scale.
- The Prospective Imagery Task (PIT) (Holmes et al., 2008; Stober, 2000) adapted for use in young people by (Pile et al., 2018). Fourteen scenarios (7 positive and 7 negative) are presented to participants (e.g. "You will achieve something you wanted to"), who are asked to imagine each happening to them and then rate this mental image on a 5-point scale; 'No image at all' to 'Very clear and detailed'.
- Autobiographical Memory Task (AMT) (Williams & Broadbent, 1986) is a measure of memory specificity. Participants will be given an example of a specific memory and then asked to give a specific memory to ten cue words (five positive; five negative).
- Screen for Child Anxiety Related Disorders (SCARED, Birmaher et al., 1997) is a self-report measure of anxiety, consisting of 41 items rated on a 3-point Likert scale.
- Rosenberg Self Esteem Scale (RSES) (Rosenberg, 1965) is a 10-item self-report measure of self-worth, rated on a 4-point Likert scale.

Statistics and data analysis

All analyses will be conducted on an intent-to-treat basis:

- Descriptive statistics: including means and standard deviations for normally and not normally distributed data will be reported for key outcomes from the feasibility RCT data

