- Recruitment and retention rates: will be described as percentages and predicted vs. actual recruitment rates will be recorded monthly
- Trial flow CONSORT diagram: will be used to show the number of approached participants, numbers eligible/ ineligible

Service user involvement

Service user advisory groups were consulted during the development of the intervention and their feedback was positive, identifying a unmet need for young people with depression and a treatment strategy that was novel to them.

Data management and dissemination

Participant data will be anonymised, and participants will be given a unique code. Consent forms will be stored separately. All anonymised data will be stored on a password-protected computer and backed up on an encrypted USB. We intend to disseminate the findings to the schools that participated in the research, as well as more widely through conferences and publications in peer-reviewed scientist journals. Following completion of the trial, the data set will be made publicly available.

Ethical issues and ethical approval

KCL ethics has granted ethical approval for the project (KCL Ethics Ref: HR-19/20-14899) to be delivered in school-settings. Ethical issues include ensuring informed consent is gained, disclosure of risk issues, confidentiality and potential to cause distress and stigma.

Informed consent: this will be sought at both the screening and intervention stages. The project will first be explained verbally to participants and they will be informed that participation is voluntary. At each stage participants will receive an information sheet which explains that they will be asked for informed consent before participation. Informed consent will be completed on Qualtrics, where participants will tick their agreement and provide their name and date of consent. This informed consent will be initially saved on Qualtrics. Should participants wish to have a copy of their consent form, it can be downloaded and saved as an encrypted file which can then be shared with the participant

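### The RCT is meant to yield initial effect-size estimates, but the Statistics section names no between-arm difference and no confidence interval for any clinical outcome

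*Combined protocol and SAP*

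**What the plan says.** The Aims section gives the RCT a purpose beyond feasibility: "The RCT will also inform on whether a full-scale efficacy trial is warranted and will provide initial estimates of effect sizes". The first secondary aim is more modest: "To gather descriptive data on symptom-change to inform sample size estimates for a future fully powered RCT of clinical and cost-effectiveness".

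The Outcome measures section lists seven secondary clinical measures (MFQ, SHAPS, PANAS, PIT, AMT, SCARED, RSES) and their timing: "Clinical outcome measures will be collected at baseline (pre), post and 3-month follow-up".

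The Statistics and data analysis section has an intent-to-treat statement and three bullets. The one that covers clinical outcomes reads: "Descriptive statistics: including means and standard deviations for normally and not normally distributed data will be reported for key outcomes from the feasibility RCT data". The other two cover recruitment and retention percentages and a CONSORT diagram. The section names no between-arm contrast, standardised effect size, baseline adjustment or confidence interval, and neither does any other section. Key outcomes are not defined.

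**The concern.** In a two-arm randomised trial with an active control, the effect size that bears on a later efficacy trial is the difference between arms. The Aims section promises such estimates, but the analysis plan names none.

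Two things follow. First, seven measures at two follow-up times give at least 7 × 2 = 14 possible effect sizes, and nothing fixes in advance which are meant. Second, an effect size computed later from summary tables could be quoted without its interval, and at this sample size the interval is wide.

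Mean change within the IMAGINE-P arm could not stand in for the contrast. The protocol reports that in an earlier school-based feasibility RCT the investigators "found that NDST improved mood, suggesting it is more ethical for randomization than a waiting list control". In addition, MFQ and SHAPS are both entry criteria and outcomes, so some change from baseline is to be expected in either arm.

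**Working it through.** **The plan's own figure.** The documents state no effect size, interval width, SD or correlation, so there is no precision figure to reproduce. The only related figure is the target of 32, with 16 per arm, which the Sample size section takes from recommended ranges and not from a formula.

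**Inputs from the documents.** 16 per arm. Drop-out is taken from the Sample size section, where the figure was "inflated to allow for drop-out following randomisation, which was estimated to be 10% based on similar studies". Applied to 32, this leaves 32 × 0.9 = 28.8 completers, or 14.4 per arm. In whole numbers that is 14 + 15, or 14 + 14 if rounded down. (The same section also speaks of inflating a sample of 50; that inconsistency is a separate matter.)

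**Assumed inputs.** The baseline-outcome correlation r is not in the documents, so a range of 0, 0.3, 0.5 and 0.7 is shown. SDs are taken as equal in the two arms, and widths are in units of the within-arm SD.

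**Step 1: unadjusted 95% half-width** = t(0.975, n1+n2−2) × √(1/n1 + 1/n2).

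- 16 + 16: 2.042 × √(2/16) = 2.042 × 0.3536 = 0.722 SD
- 14 + 15: 2.052 × √(1/14 + 1/15) = 2.052 × 0.3716 = 0.762 SD
- 14 + 14: 2.056 × √(2/14) = 2.056 × 0.3780 = 0.777 SD

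At full retention, any observed difference below 0.72 SD would therefore have an interval that includes zero.

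**Step 2: ANCOVA half-width** = t(0.975, 2n−3) × √[(2/n)(1−r²)(1 + 1/(2n−4))]. The last factor allows for average chance imbalance at baseline. At n = 16 the part that does not depend on r is 2.045 × √(0.125 × 1.0357) = 2.045 × 0.3598 = 0.736. Multiplying by √(1−r²) gives:

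| Assumed r | Half-width (SD) | Against 0.722 |
|---|---|---|
| 0 | 0.736 | 1.9% wider |
| 0.3 | 0.702 | 2.8% narrower |
| 0.5 | 0.637 | 11.7% narrower |
| 0.7 | 0.526 | 27.2% narrower |

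The two methods break even where √(1−r²) = 0.722/0.736, that is, at r of about 0.19. A simulation of 4,000 trials at each r agreed: root-mean-square half-widths were 0.737, 0.701, 0.637 and 0.524 with adjustment, and 0.721 to 0.723 without. At 14.4 per arm the adjusted half-widths are 0.782, 0.746, 0.677 and 0.558.

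**Step 3: what a reader could recover.** Arm-level means, SDs and numbers at follow-up are enough for Step 1. Step 2 also needs r. That could be recovered if the SD of change were reported alongside the baseline and follow-up SDs, but the plan lists neither r nor the SD of change.

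**The case against.** The strongest reply is that the plan suits a feasibility study. The Sample size section declines a power calculation because the purpose is feasibility, the clinical measures are secondary, and the first secondary aim asks only for descriptive change data, which the Statistics bullet supplies. The bullet's list is introduced as inclusive, so it is not closed. Intent-to-treat in a two-arm trial implies reporting by allocated arm. The raw data will also be available: "Following completion of the trial, the data set will be made publicly available".

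Most of this stands. It is why the point concerns one unnamed estimate and not a missing significance test. It does not answer the promise in the Aims section, and an open list does not say which contrast is meant.

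A reader might infer more than the documents support:

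- *That the trial could not produce an effect size at all.* Arm-level means, SDs and numbers would give an unadjusted one, and the public data set would give the rest. No data are lost.
- *That the decision on a full trial rests on a clinical effect size.* The Aims section says the RCT will inform that decision. No section ties progression to a clinical result, and the primary outcomes are feasibility and acceptability.
- *That the follow-up times are undefined.* The Outcome measures section gives them.
- *That the wide interval is itself the fault.* The width is a property of 16 per arm. Reporting the interval shows that uncertainty but does not create it, and only baseline adjustment changes it.

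**Conclusion.** The point holds as an inexpensive improvement to the plan. The Aims section promises effect-size estimates, while the Statistics section stops at means and SDs for undefined key outcomes. Followed as written, it commits to no between-arm estimate and no interval. The primary feasibility and acceptability outcomes are unaffected.

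The unadjusted half-width of 0.72 SD, or 0.76 to 0.78 SD after drop-out, rests on the documents' own numbers and on equal within-arm SDs. It is large enough that a point estimate alone would be easy to over-read. The gain from adjustment rests on an assumed correlation: it is worth having above about 0.2 and costs about 2% in width if the correlation is zero.

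**What to change.** Add to the Statistics and data analysis section:

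> For the named key clinical outcomes (for example SHAPS and MFQ) at post and at 3 months, we will report the between-arm difference by allocated arm, adjusted for the first-assessment score (ANCOVA), with a 95% CI and the number analysed per arm, as a non-confirmatory estimate without hypothesis tests.

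The team should confirm which outcomes are key. In particular, it should say whether PANAS positive affect is one of them, since the stated aim is to reduce anhedonia by improving positive affect. Naming the first-assessment score matters because MFQ and SHAPS are also completed at screening. An unadjusted difference with its 95% CI would close the gap as well, but without the gain in precision. The sentence discloses missing follow-up through the numbers analysed but does not say how it is handled; a further clause could.

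The cost is one sentence, a few small regressions on data already being collected (four if two outcomes are named at two times), one degree of freedom, and published intervals that will look wide.

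### The post-randomisation feasibility rates (n=32, 16 per arm) are to be reported as percentages without any measure of precision, although they are to inform whether a full trial should follow and how large it should be

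*Combined protocol and SAP*

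**What the plan says.** The Aims section states that the RCT will "inform on whether a full-scale efficacy trial is warranted" and will give initial effect-size estimates. Item 2 of the primary aims is "To run a feasibility RCT to evaluate recruitment and retention rates for a future efficacy RCT". The primary outcomes under Outcome measures include intervention completion, data completeness, and follow-up, adherence and questionnaire response rates.

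The Sample size section gives the planned size: "The target sample size (n=32; 16 in each arm) was determined with reference to good practice recommendations", "which recommend sample sizes of between 24 and 50". It says that "a power calculation to determine sample size is not appropriate", and that the data could inform the sample size of a later efficacy trial. It also gives the plan's only anticipated rate, "drop-out following randomisation, which was estimated to be 10" per cent, as an allowance in sizing the study.

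Statistics and data analysis consists of an intent-to-treat statement and three bullets: means and standard deviations, a CONSORT diagram, and the rates, which "will be described as percentages and predicted vs. actual recruitment rates will be recorded monthly". The documents contain no interval, precision target or progression criterion, and no figure for the predicted recruitment rate.

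**The concern.** The trial is sized for estimation and not for a test, so the precision of its estimates is the property that matters. The plan asks for point estimates of its primary outcomes and leaves the precision out.

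Two later decisions depend on these rates: whether to run a full trial, and how many participants to randomise in it. If 91% retention is observed and taken at face value, the later trial will be planned around drop-out of about 10%. If the true figure is 20% or 25%, that trial will end with fewer participants with outcome data than it needs. A percentage printed alone gives the reader no warning of this.

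**Working it through.** **Inputs.** From Sample size: n = 32, 16 per arm; drop-out 10%. My assumption: two-sided 95% confidence, because the documents give no level.

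**The plan's own figure.** The section says "The sample size of 50 was inflated to allow for drop-out following randomisation, which was estimated to be 10% based on similar studies". Inflating 50 gives 50/0.9 = 55.6, so 56, or 50 × 1.1 = 55 by the simpler method. Neither is 32. A total of 32 would follow from a base of 28 (28/0.9 = 31.1, rounded up), but no such base is stated. The target of 32 lies inside the cited range of 24 to 50. The two sentences need reconciling, but that is a separate matter. I use 32 because it is the stated target.

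**Result that matches the plan.** 32 × 0.9 = 28.8, so 29 of 32 retained (90.6%). Per arm, 16 × 0.9 = 14.4, so 14 of 16 (87.5%).

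**Exact (Clopper-Pearson) limits.** For x of n, the lower limit is the 0.025 quantile of Beta(x, n − x + 1) and the upper limit is the 0.975 quantile of Beta(x + 1, n − x).

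| Observed | Per cent | Exact 95% CI |
|---|---|---|
| 32/32 | 100 | 89% to 100% |
| 30/32 | 94 | 79% to 99% |
| 29/32 | 91 | 75% to 98% |
| 28/32 | 88 | 71% to 96% |
| 27/32 | 84 | 67% to 95% |
| 24/32 | 75 | 57% to 89% |
| 14/16 | 88 | 62% to 98% |
| 12/16 | 75 | 48% to 93% |

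For 29/32 the lower limit is 0.750, so the interval for drop-out runs from about 2% to 25%.

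**How often a reassuring result appears when retention is worse.** With X ~ Binomial(32, p), P(X ≥ 29) is 0.093 at p = 0.80 and 0.272 at p = 0.85. At twice the planned drop-out, a result at least as good as planned would still be seen about one time in eleven.

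**Consequence for a later trial.** To end with m completers, m/(1 − d) must be randomised at drop-out d. Relative to 10%, the number rises by a factor of 0.90/0.80 = 1.125 at 20% drop-out and 0.90/0.75 = 1.20 at 25%. So 29/32 leaves open a need for up to about 20% more participants than the point estimate suggests.

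**Where 32 is not the denominator.** Eligibility and recruitment rates are taken over students screened or eligible, and school uptake over schools approached. None of these numbers is stated. If, say, 100 were eligible (an assumption), 32/100 would have an interval of 23% to 42%.

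**The case against.** *Feasibility trials are descriptive, and this one reasonably declines a power calculation.* That is accepted. But an interval is a descriptive statistic and not a hypothesis test, and declining power for efficacy says nothing about the precision of the primary rates.

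*Readers can work out intervals themselves.* Largely true: a CONSORT diagram is planned and the data set will be made public, so nothing is lost for good. The plan should still present its primary results with their uncertainty, because its own conclusion will be drawn from them.

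*An interval does not make the trial more precise.* Correct. The width comes from n = 32, and reporting makes it visible without curing it.

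*The trial only informs the decision and promises no go/no-go rule.* Also correct. The absence of a numerical rule is therefore not a contradiction in the plan. Comparing predicted with actual recruitment is a partial benchmark, although the predicted figure is not given; that is a missing detail.

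A reader might go further and infer that all the primary rates are compatible with both a feasible and an infeasible trial. The documents do not support this, for three reasons. First, 32 is the denominator only for rates counted after randomisation. Second, several primary outcomes are not rates at all, such as reasons for drop-out, time needed and adverse effects. Third, the documents set no line between feasible and infeasible, and the answer depends on that line. With an assumed 80% line, every result from 24/32 to 30/32 has an interval that includes it. With an assumed 70% line, 28/32 and above exclude it, and so does the planned result of 29/32.

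**Conclusion.** The point holds for the post-randomisation rates. The plan gives them no measure of precision, and at this size the imprecision matters: a result equal to the planned 10% drop-out is compatible with drop-out of up to about 25% overall, and in one arm 14/16 retained is compatible with drop-out of up to 38%. This rests on the stated n = 32, on a 95% level (my choice), and on the target being reached.

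It does not show that the trial is too small for its purpose, or that any particular threshold is needed. The change should be made, but the trial can run without it.

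**What to change.** In Statistics and data analysis, replace the percentages-only wording for the rates with: *reported as n/N and percentage with exact (Clopper-Pearson) 95% confidence interval*. For each rate:

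- State the denominator: screened, eligible or randomised.
- Give the rate by arm as well as overall where that applies.
- Keep intervention drop-out apart from missing follow-up data. The recruitment section says that those who discontinue are still invited to assessments, so the two need not agree.

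Add a sentence saying that the progression decision will be read against the interval and not the point estimate.

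If the sponsor wants progression thresholds, it should choose them before the first randomisation and write them as proportions, because 32 may not be reached. As illustration only, take proceed at 27 or more of 32, modify at 23 to 26, and do not proceed as designed at 22 or fewer. That rule proceeds with probability 0.91 at true retention of 90%, 0.36 at 80% and 0.05 at 70%; at 70% it reaches the lowest band about half the time (0.505). The interval at 27/32 (67% to 95%) still includes 70%. These cut-offs are therefore not a recommendation. The predicted recruitment figure should be written down before recruitment starts.

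The cost is a few lines of text and no new data. The downside is that the published intervals will be visibly wide.
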